	Protocol Name:	Randomized Controlled Trial of Inferior Vena Cava Ultrasonography in the Management and Disposition of Pediatric Patients Undergoing Evaluation for Sepsis and Dehydration
	Principal Investigator:	[name] [contact] [contact] or [contact]
	Primary Contact Name/Contact Info:	[name] [contact]
	Date Revised:	2/10/2015
	Study Number:	IF1733382

- 60 ml/kg Normal Saline bolus administered within 60 minutes

Secondary

- Disposition- PICU, Floor, Discharge
- Length of ED stay (from sepsis alert to admission/discharge order entry)
- Return ED Visit for same illness
- Survival to hospital discharge
- 30 day mortality
- Left ventricular function
- Source of sepsis

For the Gastroenteritis/Dehydration arm endpoints include:

Primary

- Type of rehydration: oral versus intravenous
- Total amount of fluids given (ml amount)
- Total ED length of stay from triage time to disposition time (order to admit/discharge)

f) Procedures Involved in the Human Research

Allocation of patients to intervention and control arms will be accomplished by a computer generated randomization application Sherlock MD®. Randomization will be separate for sepsis cohort and gastroenteritis cohort. Within sepsis and gastroenteritis cohorts, subjects will be stratified by disease severity. Specifically they will meet criteria for severe sepsis or meet criteria for severe dehydration based on standard clinical severity scoring (e.g. SIRS criteria, Clinical Dehydration Score).

Subjects randomized to either arm will receive diagnostic imaging of the inferior vena cava with ultrasound. Subjects randomized to the investigational arm will undergo IVC ultrasound immediately

	Protocol Name:	Randomized Controlled Trial of Inferior Vena Cava Ultrasonography in the Management and Disposition of Pediatric Patients Undergoing Evaluation for Sepsis and Dehydration
	Principal Investigator:	[name] [contact] [contact] or [contact]
	Primary Contact Name/Contact Info:	[name] [contact]
	Date Revised:	2/10/2015
	Study Number:	IF1733382

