## Gastroenteritis Statistical Plan

We calculated the sample size required to provide more than 80% power (with a two-sided alpha level of 0.05) to detect an absolute difference of 15% in PO vs. IV rehydration or more between groups. We estimated a sample size of 200 patients for the gastroenteritis section of the study.

Enrolled Patients are to be randomized to immediate versus delayed US assessment of the IVC in patients aged 0-21 years who presented to an emergency department with vomiting requiring ondansetron or with diarrhea possibly requiring IV rehydration. Patients enrolled were randomized to assessment of dehydration by clinical exam plus US (immediate) or clinical exam alone and then US 15 minutes later (delayed). Clinical dehydration scores were recorded prior to IVC US. Decision to treat with IV versus PO rehydration, pre-test and post-test probabilities were recorded before and after US. Primary outcomes included IV versus PO rehydration based on intent-to treat principle; secondary outcomes included median total ED length of stay (EDLOS; triage time to disposition) time failure of PO rehydration, and disposition (ED discharge vs admission). All outcomes between groups were compared by using a Pearson chi-squared test. The alpha level was set at .05 for all analyses, 95% CIs were calculated, and all comparisons were two tailed. Data analysis was performed with the use of SPSS 20.0 (IBM).

We calculated the sample size required to provide more than 80% power (with a two-sided alpha level of 0.05) to detect an absolute difference of 15% more more between arms in the number of patients receiving antibiotics with 60 minutes between groups. We estimated a sample size of 200 patients for the sepsis section of the study.

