## Sepsis Statistical Plan

Enrolled Patients are to be randomized to immediate versus delayed US assessment of the IVC in patients aged 0-21 years who presented to an emergency department with a STOP SEPSIS triage alert and clinical concern for sepsis. Patients enrolled were randomized to assessment of sepsis by clinical exam plus US (immediate) or clinical exam alone and then US 15 minutes later (delayed). Pre-test probability of sepsis were recorded prior to IVC US. Decision to initial sepsis protocol/pathway, pre-test and post-test probabilities were recorded before and after US. Primary outcomes included proportion of patients receiving antibiotics within 60 minutes based on intent-to treat principle; secondary outcomes include median total ED length of stay (EDLOS; triage time to disposition), time to secured vascular access, and vasopressor use. All outcomes between groups were compared by using a Pearson chi- squared test. The alpha level was set at .05 for all analyses, 95% CIs were calculated, and all comparisons were two tailed. Data analysis was performed with the use of SPSS 20.0 (IBM).

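### Allocation is stratified by disease severity, but the SAP tests every outcome with an unstratified chi-squared test: a possible loss of power that is cheap to recover

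*Protocol*

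**What the plan says.** Protocol section 5f (Procedures Involved in the Human Research) says that allocation "will be accomplished by a computer generated randomization application", that the two cohorts are randomised separately, and then "Within sepsis and gastroenteritis cohorts, subjects will be stratified by disease severity". The criteria are severe sepsis and severe dehydration. SIRS and the Clinical Dehydration Score are named only as examples of the scoring, with no cut-off and no mention of blocking.

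The SAP's Gastroenteritis Statistical Plan says "All outcomes between groups were compared by using a Pearson chi-squared test", and its Sepsis Statistical Plan says the same: "All outcomes between groups were compared by using a Pearson chi- squared test". Neither section mentions a stratum, a covariate or an adjusted analysis.

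On severity data, the gastroenteritis section says "Clinical dehydration scores were recorded prior to IVC US". The sepsis section offers only "Pre-test probability of sepsis were recorded prior to IVC US". Both times are tied to the ultrasound, not to randomisation.

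**The concern.** Given where it stands, the severity sentence most naturally describes randomisation strata. A factor chosen for stratification is normally one expected to predict outcome. Here the primary outcomes are IV versus oral rehydration and antibiotics within 60 minutes, and both could plausibly depend on how ill the child is.

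If so, an unstratified test leaves between-stratum variation in its error term. If allocation was also balanced within strata, that variation is absent from the actual treatment contrast. Pearson then overstates the variance, and its true type I error drops below 5%. Using the category would give more power and a narrower confidence interval from the same patients.

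The available text also does not show that the category used at randomisation will reach the analysis dataset.

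**Working it through.** **Inputs from the documents.** Two-sided alpha is 0.05 and the SAP effect is 15 percentage points. On size the SAP says "We estimated a sample size of 200 patients for the gastroenteritis section of the study" and gives the same number for sepsis. I read 200 as the total (100 per arm). Protocol 5c has 200 per group for gastroenteritis, so 400 is also shown. Protocol 5c gives 58% compliance and 82 per group for sepsis.

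**Assumptions.** The documents do not give the severe share s, the outcome gap g between strata, or the blocking. All three are varied.

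**The plan's own figure.** Protocol formula for sepsis with 58% vs 78%:

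7.9 × (0.58×0.42 + 0.78×0.22) / 0.20² = 7.9 × 0.4152 / 0.04 = 82.0 per group.

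So 82 reproduces, with a 20-point effect that the text does not state.

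**Why the stratum matters.** With overall rate p, the share of outcome variance left within strata is roughly

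VR = 1 − s(1−s)g² / [p(1−p)].

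- s = 0.3, g = 0.10, p = 0.58: 1 − 0.0021/0.2436 = 0.99. Nothing to gain.
- s = 0.3, 70% vs 40% (p = 0.49): 1 − 0.0189/0.2499 = 0.92.
- s = 0.2, 80% vs 30% (p = 0.40): 1 − 0.04/0.24 = 0.83.
- s = 0.4, 80% vs 30% (p = 0.50): 1 − 0.06/0.25 = 0.76.

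**Power.** Simulation with 300,000 trials per setting, two strata, 1:1 allocation and a common odds ratio giving an average effect of ±15 points. Entries are Pearson / Cochran-Mantel-Haenszel (CMH) without continuity correction, in %, for 200 patients in total. GE is gastroenteritis; the rates are those without the treatment effect.

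| Setting | Balanced within strata | Simple randomisation | Gain (points) |
|---|---|---|---|
| Not prognostic, 58% | 61.1 / 60.6 | 60.9 / 60.5 | −0.5, −0.4 |
| 30% severe, gap 10 | 61.0 / 60.8 | 61.0 / 60.9 | −0.2, −0.1 |
| 30% severe, gap 20 | 61.2 / 62.2 | 61.0 / 62.0 | +1.0, +1.0 |
| GE, 30% severe, 70% vs 40%, +15 | 58.9 / 59.8 | 57.4 / 59.8 | +0.9, +2.4 |
| GE, 30% severe, 70% vs 40%, −15 | 59.1 / 60.9 | 58.0 / 60.8 | +1.8, +2.8 |
| GE, 20% severe, 80% vs 30%, +15 | 59.5 / 63.4 | 57.3 / 62.8 | +3.9, +5.5 |
| GE, 20% severe, 80% vs 30%, −15 | 63.8 / 70.8 | 62.2 / 70.6 | +7.0, +8.4 |
| GE, 40% severe, 80% vs 30%, +15 | 60.0 / 67.8 | 57.6 / 67.3 | +7.8, +9.7 |
| GE, 40% severe, 80% vs 30%, −15 | 59.9 / 69.5 | 57.7 / 69.1 | +9.6, +11.4 |
| Sepsis, 40% severe, 85% vs 40% | 62.0 / 68.7 | 60.9 / 68.3 | +6.7, +7.4 |

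The power near 60% follows from the assumed rates and from reading 200 as the total. It is a separate matter from stratification.

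**Other sizes.** With 400 in total, the gain is about 0 if severity is not prognostic (88.9 / 88.9). With 40% severe it is 2.6 to 4.8 points if balanced and 4.6 to 7.7 if not. In the protocol's 164-patient sepsis design (58% vs 78%, half severe, balanced, equal risk difference in each stratum), power is 79.4 / 79.4 at gap 0, 79.8 / 81.1 at gap 20 and 81.8 / 87.1 at gap 40.

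**Type I error of Pearson.** With balance, the approximation 2[1 − Φ(1.96/√VR)] at VR = 0.76 gives 2[1 − Φ(2.25)] ≈ 0.025. In simulation at 200 patients with 40% severe it is 0.029 (gastroenteritis) and 0.031 (sepsis) if balanced, and 0.052 and 0.051 if not. Uncorrected CMH stays at 0.049 to 0.053.

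**Confidence interval.** Half-width of the 95% interval for the risk difference at 200 patients, unstratified vs Mantel-Haenszel: 12.9 vs 12.9 points if not prognostic; 13.5 vs 13.1 at a 30-point gap; 13.5 vs 11.7–12.0 (gastroenteritis) and 12.9 vs 11.9 (sepsis) with 40% severe and a 45–50 point gap. The formula agrees: 13.5 × √0.76 ≈ 11.8.

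**Continuity correction.** At 200 patients, a CMH test with the 0.5 correction has 55.0% power against Pearson's 61.1% when severity is not prognostic, so the version must be named.

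**The case against.** The strongest reply is that nothing is broken. A prespecified unadjusted test after stratified allocation is valid, and the gain depends on figures that the documents do not contain. Eligibility requires that the treating physician expects benefit from intravenous fluids, which may narrow the spread of severity and of the IV/oral choice. In many plausible settings the gain is 0 to 3 points. All of this stands, and it is why the point is one of efficiency only.

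Second, stratification may mean no more than classification. The protocol names no non-severe stratum, and the immediate scan comes before full clinical assessment, so a score may not have existed at randomisation. This stands as a doubt. Randomisation strata remain the more natural reading of an allocation paragraph, and clarifying the text would settle it.

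Third, the SAP is written largely in the past tense. If outcome data were already in hand, changing the primary test would be open to selection. This too stands, as a condition on the fix.

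None of these removes the mismatch. The possible loss from stratifying is about half a point of power in the settings tested, while the possible gain is several points.

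**Conclusion.** The concern holds as a possible loss of power, not as an error of validity. The protocol stratifies by severity, and the two statistical sections of the SAP do not use the stratum; the part of the SAP before them was not available to this review. For 200 patients in total, the gain from a stratified test is nil if severity is weakly prognostic, about 1 to 3 points of power at gaps of 20 to 30 points, about 4 to 8 points with 20% severe and 80% vs 30%, and about 7 to 11 points with 40% severe and a gap of 45 to 50 points. For 400 in total the gains are smaller. Pearson's type I error falls to about 0.03 only if severity is strongly prognostic and allocation was balanced within strata, which is not stated. The direction is well supported; the size cannot be fixed from the documents. The change is worth making but not critical.

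**What to change.** In each SAP section:

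1. Make the primary test of the binary outcome a Cochran-Mantel-Haenszel test without continuity correction, or an equivalent adjusted analysis, stratified by the severity category used at randomisation. Name the exact uncorrected statistic to be read from SPSS 20.0.
2. Report a Mantel-Haenszel risk difference with its 95% confidence interval.
3. State which score and cut-off define the category, when it was assigned, and whether allocation was blocked within strata.
4. Carry the category into the analysis dataset. If it was not stored at randomisation, say so and keep the unstratified test, which remains valid.
5. Fix the change before outcomes by arm are seen. Otherwise report the stratified analysis as supportive only.

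The cost is a sentence or two per section, and no new patient data if the category was stored, which the team must confirm. The downside is at most about 1 point of power if severity is not prognostic (0.5 in the settings tested).

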All patients, regardless of age or gender, who present to the Emergency Department who trigger triage STOP SEPSIS ALERT (based on triage vital signs and chief complaint), vomiting requiring zofran or diarrhea with concern for dehydration/hypovolemia , whom the treating physician believes would benefit from intravenous fluids will be eligible for inclusion into this study. The “treating physician” refers to one of the Pediatric Emergency Medicine attendings or fellows, all of whom are listed as co-investigators on the application form submitted with this protocol. Only if and when a patient or parent expresses interest in participating in the study, the Attending or Fellow caring for the patient will determine if the patient is eligible. If the patient is eligible, and has no criteria that would exclude them from the study, written informed consent will be obtained from the guardian and assent will be obtained in children \geq 7 years old. The patient will be enrolled in the study and randomized to either the immediate ultrasonography group (US of the IVC first with before the clinician fully assesses the patient and places rehydration orders) or the control group (Ultrasonography at 15 minutes into the assessment and management of the patient).

	Protocol Name:	Randomized Controlled Trial of Inferior Vena Cava Ultrasonography in the Management and Disposition of Pediatric Patients Undergoing Evaluation for Sepsis and Dehydration
	Principal Investigator:	[name] [contact] [contact] or [contact]
	Primary Contact Name/Contact Info:	[name] [contact]
	Date Revised:	2/10/2015
	Study Number:	IF1733382

b) Inclusion and Exclusion Criteria

Inclusion criteria for enrollment in study:

All patients, regardless of age or gender, who present to the Emergency Department who:

- A. Trigger triage STOP SEPSIS ALERT (based on triage vital signs and chief complaint)
And/OR
- B. Present with vomiting requiring Zofran
And/OR
- C. Present with diarrhea with concern for dehydration/hypovolemia

whom the treating physician believes would benefit from intravenous fluids will be eligible for inclusion into this study.

Exclusion criteria for enrollment in study:

- (1) Unstable patients with life-threatening injuries who require ongoing resuscitation.
- (2) Patient undergoing traumatic resuscitation

c) Number of Subjects

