- This study does not involve medications. Dose selection procedures do not apply.
- During the process of data collection patient identifiers will be collected (first and last name, MR#, age, birth date, date of visit, notes regarding medication and fluid orders). This identifying information is necessary for US will be located on only 1 form. This form will be kept in a locked file cabinet in a locked office within Mount Sinai Hospital at all times
- Should adverse events be noted by the oversight board a suspension of this study will occur and the PPHS and IRB will be fully informed immediately of such occurrence.

MSSM Additional DSMB Member:

Indicate whether this person is the PI, a Team Member, or is Independent: Independent

 Mount Sinai	Protocol Title:	Randomized Controlled Trial of Inferior Vena Cava Ultrasonography in the Management and Disposition of Pediatric Patients Undergoing Evaluation for Sepsis and Dehydration
	Principal Investigator Name/Contact Info:	[name] [contact] [contact] or [contact]
	Primary Contact Name/Contact Info	[name] [contact]
	Date Revised:	2/10/2015
	Study Number:	IF1733382

Last Name: [name]
 First Name: [name]
 Academic Title: Associate Professor of Emergency Medicine
 Department: Emergency Medicine
 Mailing Address: [name]
 [contact]
 [contact]
 E-mail: [contact]

j) Withdrawal of Subjects

If a patient or parent expresses that they unable to tolerate the procedure, the ultrasound exam will be stopped immediately and the patient will be removed from the study. There are no infectious risks from the use of ultrasound in this study. The machine will be cleaned per routine procedure after each examination.

6) Risks to Subjects

There are no known risks to ultrasound, with no reports of adverse events in over 65 years of clinical use. The use of ultrasound is painless by avoiding contact of the ultrasound probe with the body part (solely maintaining contact with the ultrasound gel). The ability of patients to tolerate ultrasound without pain, is well documented in the literature.

7) Provisions for Research Related Injury

None

8) Potential Benefits to Subjects

More accurate diagnosis of dehydration and severe sepsis requiring emergent fluid resuscitation

9) Provisions to Protect the Privacy Interests of Subjects

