The population of interest in this study includes patients < 18 years old (i.e vulnerable subjects). All efforts will be made to protect these children during this study. As previously listed, ultrasound emits no radiation and is a painless procedure; therefore this study presents no risk to these patients. If the patient/child or parent expresses any discomfort from the ultrasound or procedure, the procedure will be immediately discontinued and the patient will be removed from the study.

When subjects with diminished mental capacity are to be enrolled, there will be an independent assessment of capacity to sign consent. If a potential participant does not have the capacity to sign consent, permission of a surrogate and assent of the potential participant if aged 7 years or greater will be obtained. If permission of the surrogate is not obtained, the potential participant will not be enrolled in the study. It is important that persons with diminished capacity be included in this study. Dehydration is clinically important and common morbidity in young children with diminished capacity (e.g. those with mental retardation/cerebral palsy). This population is particularly vulnerable to sepsis and moderate to severe dehydration requiring resuscitation and should be allowed to participate in the study.

Assent from the potential participant will be obtained for all potential participants greater than or equal to age 7 years. Consent will be obtained from parents/guardians of potential participants who are younger than 18 years of age.

15) Multi-Site Human Research (Coordinating Center)

Not applicable in this study

16) Community-Based Participatory Research

Not applicable in this study

17) Sharing of Results with Subjects

Relevant information and findings from the ultrasound imaging studies will be shared as per standard of care in the Emergency Department

18) IRB Review History

Primary application- no applicable history

 Mount Sinai	Protocol Title:	Randomized Controlled Trial of Inferior Vena Cava Ultrasonography in the Management and Disposition of Pediatric Patients Undergoing Evaluation for Sepsis and Dehydration
	Principal Investigator Name/Contact Info:	[name] [contact] [contact] or [contact]
	Primary Contact Name/Contact Info	[name] [contact]
	Date Revised:	2/10/2015
	Study Number:	IF1733382

19) Control of Drugs, Biologics, or Devices

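### Patients whose scan is stopped are to be removed from the study after randomisation, and no supplied text keeps their outcomes for the SAP's intention-to-treat primary analyses

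*Protocol*

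**What the plan says.** - **Order of events.** Protocol Section 5a: "The patient will be enrolled in the study and randomized to either the immediate ultrasonography group" or to the control group. Section 5f: "Subjects randomized to either arm will receive diagnostic imaging of the inferior vena cava with ultrasound". Every scan, and so every removal that a scan triggers, comes after randomisation.
- **Removal, first rule.** Section 5j (Withdrawal of Subjects) applies when the patient or parent says the scan cannot be tolerated: "the ultrasound exam will be stopped immediately and the patient will be removed from the study".
- **Removal, second rule.** Section 14 (Vulnerable Populations) has a lower trigger, "If the patient/child or parent expresses any discomfort from the ultrasound or procedure", and the same consequence: "the procedure will be immediately discontinued and the patient will be removed from the study".
- **Analysis principle.** The SAP's Gastroenteritis Statistical Plan puts IV versus oral rehydration on intention to treat. Its Sepsis Statistical Plan does the same for antibiotics within 60 minutes.
- **Other text on withdrawals.** Section 5i lists withdrawal rates among the things the DSMB chair monitors. Section 9 lets a subject decline participation at any point. Neither says what happens to the data.

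**The concern.** Both rules name two consequences: the scan stops, and the patient leaves the study. If leaving the study meant no more than stopping the scan, the second clause would add nothing. Staff who follow it literally could stop completing the data forms for a patient whose family never withdrew consent to data collection. The supplied SAP does not define its intention-to-treat set in a way that would prevent this.

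If removed patients are left out, the groups compared may no longer be the groups randomised. The reasons a scan is stopped, such as young age, distress or severity of illness, could plausibly relate to IV use or to antibiotic timing, although the documents do not show this. No supplied text requires stopped scans to be reported by arm, so a reader of the results could not check whether removals were few or balanced.

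**Working it through.** The plan has no figure to reproduce here. The check is a comparison of texts, followed by an illustration of size.

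**Comparison of texts**
1. Randomisation precedes the scan (Section 5a), and both arms are scanned (Section 5f). Removal under Section 5j or 14 is therefore a post-randomisation event in either arm.
2. Intention to treat needs outcomes for all randomised patients, in the arm assigned.
3. No supplied sentence says that outcomes are collected after removal, that removed patients stay in the analysis, that they are replaced, or how their missing outcomes are handled. One earlier part of the SAP was not supplied, so this silence is established only for the text available.

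**Size, on assumptions**

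From the SAP: 200 gastroenteritis patients, a 15-point target difference and a two-sided 5% test. Assumed: equal allocation (100 per arm), no true effect, IV use p = 60%, IV use among removed patients r = 80% or 90% (a gap of 20 or 30 points), and a share q removed from one arm only.

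Rate among retained patients = (p − q·r)/(1 − q), so the size of the shift = q/(1 − q) × (r − p).

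| q | q/(1 − q) | Shift, gap 20 | Shift, gap 30 | False-positive rate |
|---|---|---|---|---|
| 1% | 0.0101 | 0.20 points | 0.30 points | 5.01-5.02% |
| 2% | 0.0204 | 0.41 points | 0.61 points | 5.04-5.09% |
| 5% | 0.0526 | 1.05 points | 1.58 points | 5.26-5.58% |

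The last column is the normal approximation to the pooled two-proportion test, which is equivalent to Pearson's chi-squared test, with 100(1 − q) patients against 100. Worked case, q = 5% and r = 90%: the retained rate is (0.60 − 0.05 × 0.90)/0.95 = 58.42%, the shift is −1.58 points, the standard error is 7.04 points, and the ratio is −0.224. The rejection probability is Φ(−1.96 + 0.224) + 1 − Φ(1.96 + 0.224) = 0.0413 + 0.0145 = 5.58%.

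For scale, the standard error without removals is √(2 × 0.6 × 0.4/100) = 6.93 points. At 2% removal the larger shift is 0.61/6.97 = 0.09 standard errors, and 0.61/15 = 4% of the target difference. At 5% it is 1.58/15 = 11% of the target.

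If q and r are the same in both arms, the two shifts cancel and the difference is 0.

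Direction: if removed patients use IV fluids more often, the arm that loses them looks lower on IV use. For the sepsis outcome, the same gaps in antibiotics within 60 minutes give the same shifts, in either direction.

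**The case against.** The strongest reply is that both rules are participant-protection text. Neither mentions analysis, exclusion of data or replacement. The only text on who is analysed is the SAP, which says intention to treat. Read together, a patient could leave study procedures and still be analysed as randomised. That reading is tenable, so the conflict is conditional. It does not dispose of the point, because nothing supplied states that reading and the literal wording goes further than stopping the scan.

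Three stronger readings are tempting, and the documents support none of them.

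- **That removed patients will be dropped from the analysis.** Neither document says so. What is established is a rule that would have this effect if followed literally.
- **That removal will differ between arms.** The immediate scan is described as "US of the IVC first with before the clinician fully assesses the patient and places rehydration orders" and the control scan as "Ultrasonography at 15 minutes into the assessment and management of the patient". The points in care differ, so a difference in tolerance is conceivable. But both arms have the same scan about 15 minutes apart, and nothing shows a difference in removal.
- **That the false-positive rate is materially inflated.** Larger figures can be produced. Removing 10% from one arm gives 6.1-7.5% with the gaps used above, and 12.3% with 40% IV use overall and 90% among removed patients. These are illustrations with no basis in the documents, and none is a ceiling: an overall rate of 58% with none of the removed patients meeting the outcome gives a shift of 0.10/0.90 × 58 = 6.4 points and 14.8%.

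The opposite inference, that the protocol expects few removals, also goes too far. Section 6 says "The ability of patients to tolerate ultrasound without pain, is well documented in the literature", which concerns pain and gives no removal rate.

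It also stands that some stopped scans will be genuine withdrawals of consent, which no analysis rule can recover.

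**Conclusion.** The point holds as a conditional conflict. The protocol states a rule that, read literally, excludes patients because of a post-randomisation event, while the SAP commits both primary outcomes to intention to treat and no supplied text reconciles the two.

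Its size is unknown. On the assumptions above it is negligible at 1-2% one-arm removal, small at 5%, and zero if removal is balanced with similar outcomes. I rate it minor to should-fix. The likely bias is modest, but the correction is cheap, and without it a reader cannot tell how many patients were lost or from which arm. The rating depends on the missing part of the SAP and the consent form, neither of which was supplied, not already settling the matter.

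**What to change.** Leave the stopping of the scan exactly as it is.

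- **Protocol Sections 5j and 14.** Replace the clause on removal with: *the scan is recorded as not completed; outcomes are still collected and analysed in the randomised arm unless consent to data collection is withdrawn*.
- **Both SAP sections.** Add: *The intention-to-treat set is all randomised patients in the arm assigned, including those whose scan was stopped or not done. Stopped scans and withdrawals of consent to data collection are counted and reported by arm.*
- **Triggers.** Sections 5j and 14 use different thresholds (not tolerated; any discomfort). The investigators must reconcile them.

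The cost is a short amendment for the ethics board and a check that the consent form covers continued data collection after a stopped scan. The SAP's primary outcomes arise during the ED stay, so keeping them needs no extra visit. The later sepsis endpoints in Section 5e (return visits, survival to discharge, 30-day mortality) need only the follow-up already planned for other patients.
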